#### 4.2.9. Visit Windows

Table 3 below presents the allowable visit windows and intervals for analysis of efficacy variables. For the purposes of statistical analysis, the visit days will be recalculated in terms of study days since the first day of dosing as illustrated below.

Baseline will be defined as the last non-missing pre-treatment assessment. For post-baseline visits, if a subject has more than one assessment occurring in the same visit window, the data from the visit closest to the scheduled study day will be used. If two visits have the same distance from the scheduled study day, the data of the visit after the scheduled study day will be used.

**Table 1 Evaluation Intervals for Efficacy Analysis**

Evaluation	Protocol-Specified Interval	Interval for Analysis
Baseline (Screening and Pre-Dose)	Day -35 to Day 0	Day -35 to Day 0 (Pre-Dose)
Day 0 (Post-Dose)	Day 0 (Post-Dose)	Day 0 (Post-Dose)
Day 14	Day 11 post to Day 17 post	Day 1 post to Day 24 post
Day 28	Day 25 post to Day 31 post	Day 25 post to Day 38 post
Day 42	Day 39 post to Day 45 post	Day 39 post to Day 52 post
Day 56	Day 53 post to Day 59 post	Day 53 post to Day 66 post
Day 70	Day 67 post to Day 73 post	Day 67 post to Day 80 post
Day 84	Day 81 post to Day 87 post	Day 81 post to Day 104 post
Day 112 (Follow-Up)	Day 105 post to Day 119 post	Day 105 post to Day 119 post

Actual dates and times will be used for pharmacokinetic and pharmacodynamic analyses rather than nominal days and times.

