Treatment duration will be 12 weeks in order to optimise the duration of induction dosing for continued development. A total of 9 visits to the clinical site will include: 2 Screening visits (one for general inclusion/exclusion criteria assessment and a second including recording baseline Mayo scoring and sigmoidoscopy/ biopsy, with the latter occurring within 14 days of randomisation; Day -42 to Day -7 for both Screening visits; however, subjects may have a combined Screening visit that includes endoscopy); dose initiation (Day 0); assessment visits on Days 14, 28, 42, 56, and 84; and Follow-up visit on Day 112. Day 70 will be a phone visit and subjects will be instructed to record stool frequency and rectal bleeding data preceding Day 70. A phone visit will be conducted at approximately 6 months after the end of study treatment period in which a PML assessment will be performed. Post-treatment sigmoidoscopy/ biopsy will be performed on Day 84 (Week 12). Study design schematics for the screening/randomisation period and overall study are shown in [Figure 4-1](#) and [Figure 4-2](#), respectively. A 3-day window (± 3 days) is allowable for each study visit following dosing with a 7-day window (± 7 days) allowed for the Follow-up visit on Day 112.

Subjects will be randomised (1:1:1:1) using an interactive web/voice response system (IXRS; Almac, Craigavon, Northern Ireland) to one of the following treatments groups:

[figure not shown]
- PTG-100 (150 mg) QD by oral administration
- PTG-100 (300 mg) QD by oral administration
- PTG-100 (900 mg) QD by oral administration
- Placebo QD by oral administration

An IA will be performed after approximately 60 to 80 subjects have completed 12 weeks of dosing (Section 7.2). Subject enrolment will occur in 2 stages relative to the IA, the purpose of which will be to conduct a futility analysis and, if futility criteria are not met, to identify which study arms provide optimal data in order to select one (or 2) PTG-100 dose levels and placebo to continue enrolling subjects to the most informative dose arms.

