The schematic of the study design is displayed in Figure 4-2. The start of the study is defined as the date the first subject enrolled in the study (ie, signs an Informed Consent Form [ICF]). A subject who completes the Day 112 Follow-up visit is considered to have completed the study. Completion of the study does not include any unplanned Follow-up visits (eg, return to the clinic for repeat clinical laboratory) or the phone visit approximately 6 months after the end of treatment. The end of the study is defined as the date the last subject completes the study (or completes an Early Termination visit). The planned duration of study conduct is approximately 17 to 20 months from Screening through the final subject's Follow-up visit (up to 42 days of screening + 12- to 15-month enrolment + 12 weeks treatment + 28 days follow-up).

Figure 4-2 Study Design Schematic

Phase 2b in UC patients: 12 Week Induction
Randomised, Double-blind, Placebo-controlled Adaptive Design

ADA = anti-drug antibodies; IBDQ = Inflammatory Bowel Disease Questionnaire; PD = pharmacodynamics; PK = pharmacokinetics; QD = once daily; TNF α = tumour necrosis factor-alpha; UC = ulcerative colitis.

In this study, the primary efficacy endpoint is clinical remission as defined by the rectal bleeding, stool frequency, and endoscopic subscores of the Mayo Score; clinical response, endoscopic response, and endoscopic remission will be determined using designated subscores of the Mayo Score assessment (see [Section 7.4](#) for details). Changes in complete and partial Mayo Score, rectal bleeding subscore, stool frequency subscore, and endoscopic subscore will be evaluated at designated time points. The IBDQ questionnaire will be assessed pre- and post-treatment; sigmoidoscopy and biopsy will be performed at baseline and Day 84 for evaluation of endoscopic response and remission and histological assessment. Stool samples will be collected for faecal calprotectin at designated time points. Subject blood samples will be obtained at designated time points from Day 0 through Day 112 for analysis of safety labs, PK, PD, and ADA parameters.

Safety will be monitored with AE inquiries, assessment of concomitant medication use, clinical laboratory evaluations ([Appendix B](#)), vital sign measurements, 12-lead ECGs, and physical examination findings during the study. A PML assessment will also be done at designated time points. A study flow chart is presented in [Table 6-1](#).

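### The SAP's Week 12 window runs from 3 days early to 20 days late, so a completer's endoscopy on Days 78-80 is filed under a phone visit while one on Day 104 counts as Week 12

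*SAP*

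**What the plan says.** SAP 4.2.9 states that "the visit days will be recalculated in terms of study days since the first day of dosing", so the analysis label follows the date and not the nominal visit. Its evaluation-interval table (captioned Table 1) gives each visit a protocol interval and an analysis interval:

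- Day 70: analysis interval "Day 67 post to Day 80 post".
- Day 84: protocol interval "Day 81 post to Day 87 post", analysis interval "Day 81 post to Day 104 post".
- Day 112: both intervals "Day 105 post to Day 119 post".

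If a subject has several assessments in one window, "the data from the visit closest to the scheduled study day will be used". This rule chooses within a window; it does not move an assessment across a boundary.

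Protocol 4.1 sets the tolerance: "A 3-day window (± 3 days) is allowable for each study visit following dosing", widened to 7 days either side for Day 112. It also says that "sigmoidoscopy and biopsy will be performed at baseline and Day 84", so there is one scheduled post-treatment endoscopy. Protocol Table 6-1 and section 6.7 make Day 70 a phone visit that records only rectal bleeding and stool frequency.

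The primary endpoint (SAP 2.5.1) needs the Week 12 endoscopy subscore. The failure rule for binary endpoints (SAP 4.2.8) covers subjects who discontinue before Week 12. It does not mention a completer with no Week 12 endoscopy, who still belongs to the FAS given any post-baseline result (SAP 3.1).

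**The concern.** The primary endpoint is remission status at the end of 12 weeks of induction, and it depends on a single endoscopy. A window that stops 3 days before the target but runs 20 days past it treats two kinds of mistimed endoscopy very differently. One done 4 to 6 days early, on treatment, is lost to Week 12. One done up to 20 days late is accepted.

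The early case also creates an undefined outcome. The subject completed treatment, so the discontinuation rule does not apply. The endoscopy sits under a visit that has no endoscopic endpoint. If the Day 70 call took place on schedule, the closest-visit rule prefers it to the Day 78-80 visit, so that visit's symptom subscores are set aside too. Whether the subject is scored a failure or leaves the denominator is then open, and could be settled after the data have been seen.

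**Working it through.** **1. Reproduce the SAP's windows.** Inputs: scheduled Days 14, 28, 42, 56, 70, 84 and 112; tolerance 3 days (7 for Day 112). Rule inferred from the table: a window opens at scheduled day minus tolerance and closes the day before the next opens. The first opens at Day 1 and the last closes at 112 + 7 = 119.

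- Day 70: opens 70 − 3 = 67; closes (84 − 3) − 1 = 80.
- Day 84: opens 84 − 3 = 81; closes (112 − 7) − 1 = 104.

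All seven post-baseline windows reproduce exactly. The Week 12 window is therefore 84 − 81 = 3 days early and 104 − 84 = 20 days late.

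**2. Compare with the nearest scheduled visit.** The midpoints are 21, 35, 49, 63, 77 and 98.

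| SAP label | Strictly nearer the next visit | Tie |
|---|---|---|
| Day 14 | 22-24 | 21 |
| Day 28 | 36-38 | 35 |
| Day 42 | 50-52 | 49 |
| Day 56 | 64-66 | 63 |
| Day 70 | 78-80 | 77 |
| Day 84 | 99-104 | 98 |

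Strict mismatches: 5 × 3 + 6 = 21 days. Ties: 6. Total: 27.

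**3. Check against the protocol tolerances.** None of the 27 days falls inside any visit's protocol interval. Days 78-80, for example, lie between 70 + 3 = 73 and 84 − 3 = 81. Every visit within tolerance is labelled correctly.

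**4. Asymmetry among mistimed Week 12 visits.** The SAP accepts Days 88-104 as Week 12, which is 104 − 88 + 1 = 17 late out-of-tolerance days. It accepts no early one.

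**5. Time since last dose.** The protocol synopsis puts Day 112 about 28 days after the last dose, so the last dose is near 112 − 28 = Day 84, and Day 104 is 20 days later. Counting 84 daily doses from Day 0 (Table 6-1 footnote 19) ends on Day 83 and gives 21 days, while Table 6-1 marks dosing at Day 84. Those passages need reconciling. Neither says what a subject with a late visit takes.

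**6. Illustrative effect on power.** The documents give no frequency of early endoscopies, so this is an assumption with a range. Suppose a fraction f of subjects in both arms has an early endoscopy and is scored a non-remitter, so each rate is multiplied by (1 − f). For n = 75 per arm (the plan expects 70-80), 10% versus 31%, one-sided 0.025 and a simple two-arm comparison:

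power = Φ[(d − 1.96·SE0) / SE1], with SE0 from the pooled rate and SE1 from the separate rates.

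At f = 0: d = 0.21, SE0 = √(2 × 0.205 × 0.795 / 75) = 0.0659, SE1 = √((0.09 + 0.2139) / 75) = 0.0637, power = Φ(1.27) = 89.8%.

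| f | Rates | Power |
|---|---|---|
| 2% | 9.8% vs 30.4% | 89.0% |
| 5% | 9.5% vs 29.5% | 87.7% |
| 10% | 9.0% vs 27.9% | 85.4% |

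This is not the simulated adaptive power in SAP Table 2, which does not depend on the windows.

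**The case against.** The best defence is that the windows follow a coherent convention: each opens at the protocol tolerance and runs until the next opens. An endoscopy on Days 78-80 is already a visit deviation, and compliant visits are unaffected. Both points are true and limit the size of the problem. They do not explain the asymmetry, because Days 88-104 are deviations too and the SAP accepts them.

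A second defence is that the primary analysis is repeated in the per-protocol set, with major violations reviewed before unblinding (SAP 3.2 and 4.6.1). That helps little: endoscopy timing is not named as a criterion, and the primary FAS analysis still lacks a scoring rule.

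Several stronger readings are tempting and are not supported:

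- *Every window starts 3 days before its visit and ends 4 days before the next.* Day 14 opens at Day 1, Day 84 closes 8 days before Day 112, and Day 112 opens 7 days before its visit.
- *All 27 days are nearer another visit.* Six are ties. The SAP's tie rule concerns two assessments in one window, not the choice between windows.
- *Late endoscopies are known to be off drug.* This is inferred from the planned dosing period.
- *Midpoint windows alone cure the problem.* They would move Days 98-104 to Day 112, which has no endoscopy either, so a late completer would meet the same gap.

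**Conclusion.** The point holds for mistimed visits only. The Week 12 window is 3 days early against 20 days late; 21 of Days 1-119 go to a visit that is strictly not the nearest, and 6 more are ties. On the primary endpoint, a completer's endoscopy on Days 78-80 is lost to Week 12 with no scoring rule, while one as late as Day 104 counts. The figure of about 20 days after the last dose assumes dosing ended near Day 84.

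Subjects who discontinue before Week 12 are failures on the binary endpoints whatever the window, so there the problem concerns completers. For the continuous endpoints, an Early Termination visit dated Days 81-104 would also be labelled Week 12.

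A reader might infer that the primary result is materially biased. The documents do not support that: they give no count of mistimed endoscopies, and under the assumed 2% to 10% the loss of power is about 1 to 4 percentage points. The case for change is that a written rule misplaces primary-endpoint data and leaves an outcome undefined, and that it can be corrected cheaply before unblinding.

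**What to change.** Revise the evaluation-interval table and add an endoscopy rule to SAP 4.2.8 and 4.2.9 before unblinding.

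- **Repeated symptom, partial Mayo and calprotectin measures:** use midpoint windows. Day 14 = 1-20, Day 28 = 21-34, Day 42 = 35-48, Day 56 = 49-62, Day 70 = 63-76, Day 84 = 77-97, Day 112 = 98-119. Ties go to the later visit.
- **Endoscopy-based endpoints:** assign a non-discontinued subject's single end-of-treatment endoscopy on Days 77-97 to Week 12. Never assign it to Day 70 or Day 112.
- **Completer with no endoscopy in that range:** score as a non-remitter or non-responder in the FAS for the binary endpoints.
- **Sensitivity analysis:** repeat the endoscopy-based analyses accepting endoscopies up to Day 104.

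The cost is one SAP table and a short rule, with no new data and no change in conduct. The downside is that any endoscopies on Days 98-104 no longer count in the main analysis. The Week 12 range would still be uneven, 7 days early to 13 days late, but the latest accepted endoscopy moves from 20 days after Day 84 to 13.

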### 4.3. Interim Analyses

An unblinded interim analysis (IA) will be performed by the ADRC after approximately 60-80 subjects have completed the full 12 weeks dosing. A futility analysis will be performed; if the trial does not meet criteria for futility, further analysis will be conducted in order to drop one (or two) of the PTG-100 dose arms. Following the IA, randomization will continue to the remaining dose arms (Stage 2).

Conditional power will also be computed at the IA. It is the probability that the trial will yield a statistically significant difference for clinical remission at the higher chosen dose for Stage 2 if the observed difference at the IA is the TRUE underlying difference and the trial is continued to completion. If this probability is less than 10%, the ADRC could suggest that the trial be stopped for futility after review of safety and other efficacy and exploratory endpoints. Conditional power for an active dose versus placebo is derived as follows.

Let  $\hat{\delta}_2$  be the observed difference of proportions between the active dose and placebo group based on data from the second stage. Then  $p_2 = \Phi\left(\frac{\hat{\delta}_2}{SE(\hat{\delta}_2)}\right)$ . Therefore

$$\Phi\left(\frac{\hat{\delta}_2}{SE(\hat{\delta}_2)}\right) \leq \Phi\left\{\frac{\Phi^{-1}(\alpha) - w_1\Phi^{-1}(\tilde{p}_1)}{w_2}\right\}$$

or equivalently

$$\frac{\hat{\delta}_2}{SE(\hat{\delta}_2)} \leq \frac{\Phi^{-1}(\alpha) - w_1\Phi^{-1}(\tilde{p}_1)}{w_2}$$

Denote the true difference of response rates between the selected active dose and placebo group by  $\delta$ . Then we have

$$\frac{\hat{\delta}_2 - \delta}{SE(\hat{\delta}_2)} \leq \frac{\Phi^{-1}(\alpha) - w_1 \Phi^{-1}(\tilde{p}_1)}{w_2} - \frac{\delta}{SE(\hat{\delta}_2)}$$

Note that  $\frac{\hat{\delta}_2 - \delta}{SE(\hat{\delta}_2)}$  follows an approximately standard normal distribution. Hence the conditional power is given by

$$\begin{aligned} P \left\{ \frac{\hat{\delta}_2 - \delta}{SE(\hat{\delta}_2)} \leq \frac{\Phi^{-1}(\alpha) - w_1 \Phi^{-1}(\tilde{p}_1)}{w_2} - \frac{\delta}{SE(\hat{\delta}_2)} \right\} \\ = \Phi \left\{ \frac{\Phi^{-1}(\alpha) - w_1 \Phi^{-1}(\tilde{p}_1)}{w_2} - \frac{\delta}{SE(\hat{\delta}_2)} \right\} \end{aligned}$$

where  $SE(\hat{\delta}_2) = \sqrt{\frac{\pi_t(1-\pi_t)}{n_{2t}} + \frac{\pi_c(1-\pi_c)}{n_{2c}}}$  and  $n_{2t}, n_{2c}$  are the number of subjects for the active dose and placebo group at the second stage respectively. Since we don't know  $\delta, \pi_t, \pi_c$ , we will replace them by those observed from the first stage data in the conditional power calculation.

PD, efficacy, and safety data will be analyzed to model dose- and exposure-response from Stage 1 of the trial to allow dropping of an ineffective or redundant arm(s). It is also possible that a new dose arm (not tested in Stage 1 of the trial) could be added in Stage 2 for exploratory purposes. Since the trial provides for a 12-week treatment period, it is expected that an additional approximately 60 subjects would be randomized in equal proportions to the 4 treatment groups while the first approximately 60-80 subjects' 12-week data are accumulated and analyzed. Hence, in Stage 2 the remaining subjects would be randomized in equal proportions to the selected dose(s) and placebo. This would yield approximately 70-80 subjects per treatment group for the selected doses. The final analysis will combine all observed data from both Stages 1 and 2.

Dose selection will further be made in consideration of safety data and sound clinical judgment, and will be made by the ADRC), which will be comprised of the DMC and a representative of the Sponsor (not involved in the direct conduct of the study). No pre-specified algorithm will be defined for the IA. Only the ADRC, which will make the dose selection for Stage 2, and the Independent Statistical Center, which will perform the IA, will be unblinded.

#### 4.4. Subject Disposition

Subject disposition will be tabulated, including the number screened, the number randomized by treatment group, the number with major protocol violations, the number in each subject population for analysis, the number that withdrew prior to completing the study, and reasons for withdrawal.

The disposition by study visit tabulation will be based on the FAS population in order to report specifically on the disposition of dosed subjects with endpoint data.

Disposition will also be presented graphically in the study report using a CONSORT diagram, utilizing frequencies from validated tabular outputs.

A by-subject listing of study completion information, including the reason for premature study withdrawal, if applicable, will be presented.

#### **4.5. Demographic and Baseline Characteristics**

Baseline, demographic, medical history, and physical examination at screening information will be summarized for the safety population using descriptive statistics. No formal statistical comparisons will be performed. These variables will also be summarized by analysis stage (1 vs. 2), both overall and restricted to the placebo group. Baseline disease characteristics from the sigmoidoscopy, biopsy, and a baseline Complete Mayo Score will also be summarized by analysis stage, both overall and restricted to the placebo group.

Demographic and Baseline data will be provided in data listings.

A by-subject listing of all medical history conditions and physical examination documented at screening for the randomized population will be provided.

Exposure to study drug will be summarized by treatment group for the safety population. Exposure will be summarized by total amount of time in the study and total number of days on study drug. A by-subject listing of exposure to study drug for all randomized subjects will also be provided.

#### **4.6. Efficacy Evaluations**

##### **4.6.1. Primary Efficacy Analysis**

The primary efficacy endpoint for this study is the proportion of subjects receiving PTG-100 with clinical remission at Week 12 compared with placebo, as defined in Section 2.5.1.

Efficacy analysis for the primary endpoint will be conducted using the FAS population and will be repeated on the PP population as a sensitivity analysis.

The proportion of subjects with clinical remission at Week 12 will be calculated and reported with a two-sided 95% exact confidence interval as an estimate of the true proportion of subjects with clinical remission in the target patient population. Two approaches will be used to report the percentages:

Approach 1: The naïve percentage and associated 95% CI for each dose group, based on data combined across both stages of the trial.

Approach 2: For doses that are selected for Stage 2, the Stage 2-only proportion of subjects with clinical remission and 95% CI will be reported. For doses not selected for Stage 2, the proportions and associated 95% CI based on Stage 1 data only will be reported.

Analysis to examine treatment effect (i.e. odds ratio for clinical remission among subjects with each active dose vs. placebo and 95% CI) will be carried out at the Week 12 time point, employing a Cochran-Mantel-Haenszel test stratified for prior TNF- $\alpha$  use (yes/no). Raw p-values, unadjusted for multiple comparisons, associated with each odds ratio will also be presented.

To obtain the primary endpoint study p-values, Simes-adjusted p-values for each dose regimen vs. placebo that are produced for the primary endpoint from the first and second stages of the study will be combined by using the inverse normal combination function to obtain the final p-value.

The components contributing to the Stage 1 portion of the p-value will include data of subjects from all 4 original dose groups (placebo, low, medium, high dose) who were enrolled during Stage 1, defined as on or before the data snapshot date for the interim look at efficacy.

The components contributing to the Stage 2 portion of the p-value will be data from subjects from the dose groups that were not discontinued who were enrolled after the date of the data snapshot for the interim look at efficacy.

The final p-value for the trial primary endpoint will be a weighted combination of the two components, as described below.

The null hypothesis to be tested is

$$H_0: \pi_C = \pi_L = \pi_M = \pi_H$$

against the alternative hypothesis

$$H_1: \text{at least one of } \pi_L, \pi_M, \pi_H \text{ is different from } \pi_C$$

where  $\pi_C$  is the response rate for placebo arm, and  $\pi_L, \pi_M, \pi_H$  are the response rates for the three active dose groups. Let  $w_1 = \sqrt{t_1}$  and  $w_2 = \sqrt{1 - t_1}$  be the prespecified weights where  $t_1$  is the statistical information time for interim analysis. Let  $p_{1L}, p_{1M}, p_{1H}$  be the marginal p-values for the three comparisons based on the test statistics of difference of proportions between active dose and placebo group. The test is left tailed. Let  $p_{1(1)} \leq p_{1(2)} \leq p_{1(3)}$  be the ordered p-values. Let  $\tilde{p}_1$  be the Simes adjusted p-value based on the first stage data. Then

$$\tilde{p}_1 = \min\{3p_{1(1)}, \frac{3}{2}p_{1(2)}, p_{1(3)}\}.$$

Let  $p_2$  be the p-value for the comparison for the selected dose versus placebo group. The final combined Simes p-value is given by

$$\Phi(w_1\Phi^{-1}(\tilde{p}_1) + w_2\Phi^{-1}(p_2))$$

where  $\Phi(\cdot)$  is the cumulative distribution function of standard normal variable and  $\Phi^{-1}(\cdot)$  is the inverse cumulative distribution function of standard normal variable.

The final analysis is significant if

$$\Phi(w_1\Phi^{-1}(\tilde{p}_1) + w_2\Phi^{-1}(p_2)) \leq \alpha$$

which is the same as

$$p_2 \leq \Phi \left\{ \frac{\Phi^{-1}(\alpha) - w_1 \Phi^{-1}(\tilde{p}_1)}{w_2} \right\}$$

Analyses of the primary endpoint will be conducted separately for the subjects with prior TNF-alpha use and those without prior TNF-alpha use. Treatment effect estimates will be reported using the naïve odds ratio estimator and its associated 95% CI. P-values will be derived from unstratified Cochran-Mantel-Haenszel tests.

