6.11 Efficacy Assessments

6.11.1 Mayo Score

Clinical remission, clinical response, endoscopic response, endoscopic remission, complete and partial Mayo Score and individual endoscopy, rectal bleeding, and stool frequency subscores will be assessed using the Mayo Score (see [Appendix A](#)).

Subjects will record stool frequency and rectal bleeding subscores in an electronic subject diary each day through the entire treatment and follow-up periods. Subjects will be provided standardised instructions for recording the number of stools and their worst rectal bleeding over a 24-hour period ([Appendix A](#)). Each subscore ranges from 0 to 3, with higher scores indicating more severe disease. For visits that include a sigmoidoscopy, data collected on the day of the bowel preparation will not be used to assess the Mayo Score. The nearest 3 available days preceding the study visit (or bowel preparation) will be used to assess the Mayo Score, allowing for discontinuous days if a day is missing (eg, Day -4, Day -3, Day -1 [with Day -2 missing]). However, if the subject has a combined Screening visit, then the baseline Mayo Score for stool frequency and rectal bleeding should be done before the day of randomization for final determination of eligibility.

Endoscopic subscore will be assessed by a central reading of recorded endoscopy scans. Sigmoidoscopy will be performed by the site endoscopist and scored by a blinded central reader reviewing video recordings of the procedure. Further details to standardise procedures, video recordings/equipment, and assessment of endoscopy will be provided in the laboratory manual.

The complete Mayo Score is a sum of 4 subscores (ie, stool frequency, rectal bleeding, endoscopic findings, and PGA). The complete Mayo Score ranges from 0 to 12 using all 4 subscores.

Partial Mayo Score (range 0 to 9) will include the PGA, stool frequency, and rectal bleeding subscores only.

At baseline and Day 84 (or Early Termination), complete Mayo Score will be assessed and recorded.

For evaluation of the primary endpoint clinical remission, the PGA subscore will **not** be evaluated, only the stool frequency, rectal bleeding, and endoscopic subscores will be assessed ([Section 7.4](#)). Clinical response will be assessed using the stool frequency and rectal bleeding subscores.

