7 DATA ANALYSES AND SAMPLE SIZE

7.1 Sample Size

Approximately 240 male and non-gravid female subjects aged 18 to 80 with moderate to severe active UC will be randomised. If only 2 arms are selected for continuation following the IA, then up to approximately 210 subjects will be randomised in the study; see [Section 7.2](#).

Prior studies^{1,17-21} suggest treatment effects of approximately 21 percentage point differences from placebo clinical remission rate of approximately 10%. Those values were assumed for purposes of design of this 12-week trial.

The table below shows power for representative scenarios of potential TRUE underlying dose-response relationships, as well as that for no drug effect to assess type 1 error (calculations via Cytel's EAST COMPASS adaptive dose-finding software based on 1000 simulations of each design, with each simulated trial analysed as described in the statistical methods section).²²

TRUE underlying response rates				power (alpha=0.025, 1-sided)			
placebo	150 mg	300 mg	900 mg	N=260	N=240	N=220	N=200
0.1	0.2	0.31	0.31	93%	91%	90%	84%
0.1	0.17	0.24	0.31	83%	82%	78%	75%
0.1	0.1	0.1	0.1	3.4%	2.2%	1.7%	2.1%

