## 4. STATISTICAL METHODS

### 4.1. Sample Size Justification

Approximately 240 male and non-gravid female subjects aged 18-80 with moderate to severe active UC will be randomized.

Prior studies suggest treatment effects of ~21 percentage point differences from placebo clinical remission rate of ~10%. Those values were assumed for purposes of design of this 12-week treatment trial.

Table 2 below shows power for representative scenarios of potential TRUE underlying dose-response relationships, as well as that for no drug effect to assess type 1 error (calculations via Cytel's EAST COMPASS adaptive dose-finding software based on 1000 simulations of each design, with each simulated trial analyzed as described in Section 4.6).

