**Table 2 Power and Type 1 Error for Various Response Rates**

TRUE underlying response rates				power (alpha=0.025, 1-sided)			
placebo	150 mg	300 mg	900 mg	N=260	N=240	N=220	N=200
0.1	0.2	0.31	0.31	93%	91%	90%	84%
0.1	0.17	0.24	0.31	83%	82%	78%	75%
0.1	0.1	0.1	0.1	3.4%	2.2%	1.7%	2.1%

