### 4.2. General Statistical Methods and Data Handling

#### 4.2.1. General Methods

All output will be incorporated into Microsoft Excel or Word files, sorted and labeled according to The International Council for Harmonisation of Technical Requirements for Pharmaceuticals for Human Use (ICH) recommendations, and formatted to the appropriate page size(s).

Tabulations will be produced for appropriate demographic, baseline, efficacy, pharmacokinetic, pharmacodynamic and safety parameters. For categorical variables, summary tabulations of the number and percentage within each category (with a category for missing data) of the parameter will be presented. For continuous variables, the mean, median, standard deviation, minimum and maximum values will be presented.

Formal statistical hypothesis testing will be performed on the primary efficacy endpoint with all tests conducted at the 1-sided, 0.025 level of significance. Summary statistics will be presented, as well as confidence intervals on selected parameters, as described in the sections below.

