#### 4.2.4. Adjustments for Covariates

The analyses may be adjusted for the randomization stratification factor, prior treatment with TNF- $\alpha$  antagonist. It will be used in the stratified primary efficacy analysis, and as a covariate in models used for continuous endpoints.

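### Adjusting the primary remission test for baseline Mayo score is a cheap efficiency gain, probably 1 to 3 points of power; the planned CMH test is valid without it

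*SAP*

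**What the plan says.** SAP 4.6.1 estimates the odds ratio for remission at Week 12 for each dose against placebo, "employing a Cochran-Mantel-Haenszel test stratified for prior TNF"-α use. Later in the same section, the marginal p-values that enter the Simes adjustment and the inverse-normal combination are "based on the test statistics of difference of proportions between active dose and placebo group"; no covariate is named there. SAP 4.2.4 names one adjustment variable, the randomisation stratum: "It will be used in the stratified primary efficacy analysis, and as a covariate in models used for continuous endpoints". Protocol 7.4 likewise specifies a CMH test adjusted for stratification factors.

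The baseline score is available. Protocol 5.1 (criterion 3) and the notes to Table 6-1 require a complete Mayo score of 6 to 12 before randomisation, and Protocol 6.11.1 states: "At baseline and Day 84 (or Early Termination), complete Mayo Score will be assessed and recorded". SAP 4.6.2 adjusts the continuous secondary endpoints for baseline values. It analyses the binary secondary endpoints in the same way as the primary, so these also omit baseline severity. Neither document gives a reason.

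**The concern.** Remission is defined from stool frequency, rectal bleeding and endoscopy, three of the four components of the baseline Mayo score. A baseline measure so close to the outcome may predict it. If it does, an unadjusted comparison leaves removable variance in the test.

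Chance imbalance adds to this. Stage 1 has 60 to 80 subjects over four arms, or 15 to 20 per arm. The standard error of a standardised baseline difference between two arms is √(2/n): 0.37 SD at n=15 and 0.32 SD at n=20. A given dose-placebo pair would therefore differ by 0.3 SD or more by chance about 41% or 34% of the time. The unadjusted Stage 1 result feeds both the Simes p-value and the conditional power used for futility. At stake is a modest amount of power, not the validity of the result.

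**Working it through.** **Inputs from the documents.** One-sided alpha 0.025 (SAP 4.2.1: "all tests conducted at the 1-sided, 0.025 level of significance"). Protocol 7.1 assumes "treatment effects of approximately 21 percentage point differences from placebo clinical remission rate of approximately 10" per cent, so 10% against 31%. The SAP 4.1 power table ("Table 2 Power and Type 1 Error for Various Response Rates") gives, at N=240, 91% for true rates 0.1/0.2/0.31/0.31 (scenario 1), 82% for 0.1/0.17/0.24/0.31 (scenario 2) and 2.2% under the null, "based on 1000 simulations of each design".

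**Inputs assumed.** Baseline Mayo 6 to 12 with SD 1.58; odds ratio for remission per Mayo point from 1 to 0.4; the two best observed doses continue; stage weights are the root of the information fraction. Marginal remission rates stay at the documents' values.

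**1. Reproduce the plan's power.** Stage 1 of 60 (15 per arm) plus an overrun of 60 (15 per arm) leaves 240 − 120 = 120 subjects for three arms, or 40 each. Continuing arms end with 15 + 15 + 40 = 70, within the planned 70 to 80. Simulation of the closed Simes, inverse-normal design with unadjusted tests (6000 trials per scenario) gave 90.2% against 91%, 80.5% against 82%, and 1.7% under the null against 2.2%. The plan's own simulation error is √(0.91×0.09/1000) = 0.9 points and √(0.82×0.18/1000) = 1.2 points. With Stage 1 of 80, the two powers are 88.8% and 78.6%. The N=200 column did not reproduce (80.9% and 69.4% against 84% and 75%); the stage sizes behind that column are not stated.

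**2. Variance needed for a 5-point gain.** Let μ = z(power) + 1.96. The information ratio needed is (μ_new/μ_old)², and the share of outcome variance to be explained is 1 − 1/ratio.
- 82% to 87%: (3.086/2.875)² = 1.152, so 13%.
- 91% to 96%: (3.711/3.301)² = 1.264, so 21%.

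**3. What a baseline score can explain.** For one dose against placebo at 70 per arm, SE = √[(0.10×0.90 + 0.31×0.69)/70] = 0.0659. Then 0.21/0.0659 = 3.187 and power = Φ(3.187 − 1.96) = 89.0%. With relative efficiency RE, adjusted power = Φ(3.187√RE − 1.96). For example, RE 1.089 gives Φ(3.326 − 1.96) = 91.4%.

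| Odds ratio per point | AUC | Placebo remission, Mayo 6 / 12 | RE | Pairwise, formula | Pairwise, logistic LR (simulated) |
|---|---|---|---|---|---|
| 1 | 0.50 | 10% / 10% | 1.000 | 89.0% | 89.5→89.4% |
| 0.8 | 0.60 | 16% / 5% | 1.018 | 89.5% | 88.6→89.4% |
| 0.7 | 0.65 | 20% / 3% | 1.045 | 90.3% | 88.8→90.8% |
| 0.6 | 0.70 | 25% / 2% | 1.089 | 91.4% | 89.0→91.7% |
| 0.5 | 0.76 | 31% / 0.7% | 1.155 | 92.9% | 88.6→93.0% |
| 0.4 | 0.81 | 38% / 0.3% | 1.251 | 94.6% | not run |

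At an odds ratio of 0.6 the score explains only about 5% of outcome variance on placebo and 11% on active.

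**4. Full two-stage design, gain in points.** Two versions of the adjusted test were run. The first is a linear-residual score test (4000 trials per cell). The second uses a pooled null variance.

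| Odds ratio per point | Score test, scenario 1 / 2 | Pooled null variance |
|---|---|---|
| 1 | −1.2 / −1.4 | about 0 |
| 0.8 | +0.2 / −1.0 | about +1 |
| 0.7 | +0.4 / +0.4 | +1 to +2 |
| 0.6 | +1.5 / +1.3 | +2 to +3 |
| 0.5 | +3.1 / +3.8 | +3 to +5 |

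The score test loses 1.2 to 1.4 points when the covariate is useless. Adding that back gives 1.5 + 1.2 = 2.7 and 1.3 + 1.4 = 2.7 at an odds ratio of 0.6, and 4.3 and 5.2 at 0.5. Simulation error is about 0.5 points. Type 1 error was 1.8% for the score test (odds ratio 0.7) and 1.6 to 2.2% in the pooled-variance run.

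**The case against.** A reader might infer that the trial gives up 5 or more points of power if baseline severity is a reasonably strong predictor. A correlation of 0.5 put into the normal approximation does take 82% to Φ(2.875/√0.75 − 1.96) = 91%. The documents do not support that reading. They report no association between baseline Mayo and remission, and such a correlation is extreme for a rare binary outcome. With a normal score, the correlation cannot exceed 0.585 at a 10% rate. A value of 0.5 on placebo would need an AUC of 0.94, and 0.4 would need 0.86.

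Nor does sharing components with the outcome establish strong prediction. Entry restricts the total to 6 to 12 and endoscopy to 2 or 3. The total includes the physician's global assessment, which remission ignores. Remission also requires a stool-frequency fall of at least 1, so a subject who starts at 0 cannot remit.

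Three further points stand. The gain beyond the anti-TNF stratum was not estimated and could be smaller. Stage 1 expects only 15 × 0.10 = 1.5 to 20 × 0.10 = 2 placebo remissions, so a stage-wise logistic model would be unstable. The change also reaches past SAP 4.6.1 into the protocol and the conditional-power formula. These points limit the size and shape the fix. They do not remove the benefit of using a value that is already collected.

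**Conclusion.** The omission is confirmed and unexplained, but it is an optional efficiency improvement. The CMH test controls its error rate without baseline Mayo, and nothing here suggests bias. At N=240 the likely gain is roughly 1 to 3 points of power for odds ratios of 0.8 to 0.6 per Mayo point. The less favourable score-test version gives −1.0 to +1.5 over the same range. About 5 points requires an odds ratio of about 0.5 or stronger, meaning placebo remission falling from 31% at Mayo 6 to under 1% at Mayo 12. All of this rests on assumed prognostic strength, baseline distribution, dose-selection rule and stage weights, so confidence in the size is low.

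**What to change.** Before unblinding, pre-specify in SAP 4.6.1 and 4.2.4 that each stage-wise p-value comes from a linear covariate-adjusted difference of proportions. Fit it over all arms in that stage (in Stage 2, the continuing arms, as the SAP already defines), with terms for treatment, prior anti-TNF stratum and baseline complete Mayo score. Name the variance estimator, since it decides whether a useless covariate costs power. Enter the p-values into the same Simes and inverse-normal combination. Do not use a stage-wise logistic model. Use the same approach for clinical response, endoscopic response and endoscopic remission, and keep the stratified CMH odds ratio as the supportive analysis.

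Align Protocol 7.4, SAP section 5 (which declares no changes from the protocol) and the standard error in the SAP 4.3 conditional-power formula. If the sponsor prefers CMH as primary, the adjusted analysis can be pre-specified as supportive, with a sentence explaining the choice.

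The cost is document edits and modest programming, with no new data. The downside is about 1 point of power if baseline Mayo is not prognostic (1.2 to 1.4 in the less favourable run, none with the pooled null variance).
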